### 11.1.3 Expectedness

Adverse events can be 'Expected' or 'Unexpected.'

#### 11.1.3.1 Expected adverse event

Expected adverse events are those that have been previously identified as resulting from administration of the agent. For the purposes of this study, an adverse event is considered expected when it appears in the current adverse event list, the Investigator's Brochure, the package insert or is included in the informed consent document as a potential risk.

Refer to Section 6.1 for a listing of expected adverse events associated with the study agent(s).

#### 11.1.3.2 Unexpected adverse event

For the purposes of this study, an adverse event is considered unexpected when it varies in nature, intensity or frequency from information provided in the current adverse event list, the Investigator's Brochure, the package insert or when it is not included in the informed consent document as a potential risk.

#### 11.1.4 Attribution

Attribution is the relationship between an adverse event or serious adverse event and the study treatment. Attribution will be assigned as follows:

- Definite – The AE is clearly related to the study treatment.
- Probable – The AE is likely related to the study treatment.
- Possible – The AE may be related to the study treatment.
- Unlikely - The AE is doubtfully related to the study treatment.
- Unrelated - The AE is clearly NOT related to the study treatment.

### 11.2 Procedures for AE and SAE Recording and Reporting

Reporting Participating investigators will assess the occurrence of AEs and SAEs at all participant evaluation time points during the study.

All AEs and SAEs whether reported by the participant, discovered during questioning, directly observed, or detected by physical examination, laboratory test or other means, will be recorded in the participant's medical record and on the appropriate study-specific case report forms.

Except as described in Section 4.2.1.5, the descriptions and grading scales found in the CTEP Active Version of the NCI Common Terminology Criteria for Adverse Events (CTCAE) will be utilized for AE reporting. The CTEP Active Version of the CTCAE is identified and located on the CTEP website at:

[http://ctep.cancer.gov/protocolDevelopment/electronic\\_applications/ctc.htm](http://ctep.cancer.gov/protocolDevelopment/electronic_applications/ctc.htm).

All appropriate treatment areas should have access to a copy of the CTEP Active Version of CTCAE.

### **11.3 Reporting Requirements**

For multi-site trials where a DF/HCC investigator is serving as the principal investigator, each participating investigator is required to abide by the reporting requirements set by the DF/HCC. The study must be conducted in compliance with FDA regulations, local safety reporting requirements, and reporting requirements of the principal investigator.

Each investigative site will be responsible to report SAEs that occur at that institution to their respective IRB. It is the responsibility of each participating investigator to report serious adverse events to the study sponsor and/or others as described below.

### **11.4 Reporting to the Study Sponsor**

#### **11.4.1 Serious Adverse Event Reporting**

All serious adverse events that occur after the initial dose of study treatment, during treatment, or within 30 days of the last dose of treatment must be reported to the DF/HCC Overall Principal Investigator on the local institutional SAE form. This includes events meeting the criteria outlined in Section 11.1.2, as well as the following:

- Grade 2 (moderate) and Grade 3 (severe) events that are unexpected and at least possibly related/associated with the intervention.
- All Grade 4 (life-threatening or disabling) events unless expected AND specifically listed in the protocol as not requiring expedited reporting.
- All Grade 5 (fatal) events while the participant is enrolled and actively participating in the trial OR when the event occurs within 30 days of the last study intervention.

Note: If the participant is in long term follow up, report the death at the time of continuing review.

Participating investigators must report each serious adverse event to the DF/HCC Overall Principal Investigator within 24 hours of learning of the occurrence. In the event that the participating investigator does not become aware of the serious adverse event immediately (e.g., participant sought treatment elsewhere), the participating investigator is to report the event within 24 hours after learning of it and document the time of his or her first awareness of the adverse event. Report serious adverse events by telephone, email or facsimile to:

[name].  

Within the following 24-48 hours, the participating investigator must provide follow-up information on the serious adverse event. Follow-up information should describe whether the event has resolved or continues, if and how the event was treated, and whether the participant will continue or discontinue study participation.

#### 11.4.2 Non-Serious Adverse Event Reporting

Non-serious adverse events will be reported to the DF/HCC Overall Principal Investigator on the toxicity Case Report Forms.

### **11.5 Reporting to the Institutional Review Board (IRB)**

Investigative sites within DF/HCC will report all serious adverse events directly to the DFCI Office for Human Research Studies (OHRS).

Other investigative sites should report serious adverse events to their respective IRB according to the local IRB's policies and procedures in reporting adverse events. A copy of the submitted institutional SAE form should be forwarded to:

[name].

The DF/HCC Principal Investigator will submit SAE reports from outside institutions to the DFCI Office for Human Research Studies (OHRS) according to DFCI IRB policies and procedures in reporting adverse events.

### **11.6 Reporting to Hospital Risk Management**

Participating investigators will report to their local Risk Management office any subject safety reports or sentinel events that require reporting according to institutional policy.

### **11.7 Monitoring of Adverse Events and Period of Observation**

All adverse events, both serious and non-serious, and deaths that are encountered from initiation of study intervention, throughout the study, and within 30 days of the last study intervention should be followed to their resolution, or until the participating investigator assesses them as stable, or the participating investigator determines the event to be irreversible, or the participant is lost to follow-up. The presence and resolution of AEs and SAEs (with dates) should be documented on the appropriate case

report form and recorded in the participant's medical record to facilitate source data verification.

For some SAEs, the study sponsor or designee may follow-up by telephone, fax, and/or monitoring visit to obtain additional case details deemed necessary to appropriately evaluate the SAE report (e.g., hospital discharge summary, consultant report, or autopsy report).

Participants should be instructed to report any serious post-study event(s) that might reasonably be related to participation in this study. Participating investigators should notify the DF/HCC Overall Principal Investigator and their respective IRB of any unanticipated death or adverse event occurring after a participant has discontinued or terminated study participation that may reasonably be related to the study.

## 12 DATA AND SAFETY MONITORING

### 12.1 Data Reporting

#### 12.1.1 Method

The ODQ will collect, manage, and monitor data for this study.

#### 12.1.2 Data Submission

The schedule for completion and submission of case report forms (paper or electronic) to the ODQ is as follows:

Form	Submission Timeline
Eligibility Checklist	Complete prior to registration with ODQ

On Study Form	Within 14 days of registration
Lab Form	Within 14 days of registration; and within 14 days of protocol defined laboratory assessment
Tumor Measurement/Staging Form	Within 14 days of registration; and within 14 days of protocol defined restaging assessment
Chemotherapy Treatment Form	Within 10 days of the last day of the cycle of FOLFIRINOX-Losartan therapy
Chemoradiation Treatment Form	Within 10 days of completion of combined capecitabine and proton radiation
Toxicity/Adverse Event Report Form	Every two weeks during FOLFIRINOX - Losartan; weekly during chemoradiation; and within 14 days of protocol defined follow up visit
Surgery/Pathology Form	Within 14 days of surgery, if applicable
Off Treatment/Off Study Form	Within 14 days of completing treatment or being taken off study for any reason
Follow up/Survival Form	Within 14 days of the protocol defined follow up visit date

## 12.2 Safety Meetings

The DF/HCC Data and Safety Monitoring Committee (DSMC) will review and monitor toxicity and accrual data from this trial. The committee is composed of clinical specialists with experience in oncology and who have no direct relationship with the study. Information that raises any questions about participant safety will be addressed with the Principal Investigator and study team.

The DSMC will meet as required to review toxicity and accrual data. Information to be provided to the committee may include: up-to-date participant accrual; current dose level information; DLT information; all grade 2 or higher unexpected adverse events that have been reported; summary of all deaths occurring within 30 days for Phase I or II protocols; for gene transfer protocols, summary of all deaths while being treated and during active follow-up; any response information; audit results, and a summary provided by the study team. Other information (e.g. scans, laboratory values) will be provided upon request.

### **12.3 Monitoring**

Involvement in this study as a participating investigator implies acceptance of potential audits or inspections, including source data verification, by representatives designated by the DF/HCC Overall Principal Investigator (or Protocol Chair) or DF/HCC. The purpose of these audits or inspections is to examine study-related activities and documents to determine whether these activities were conducted and data were recorded, analyzed, and accurately reported in accordance with the protocol, institutional policy, Good Clinical Practice (GCP), and any applicable regulatory requirements.

All data will be monitored for timeliness of submission, completeness, and adherence to protocol requirements. Monitoring will begin at the time of participant registration and will continue during protocol performance and completion.

## **13 REGULATORY CONSIDERATIONS**

### **13.1 Protocol Review and Amendments**

This protocol, the proposed informed consent and all forms of participant information related to the study (e.g., advertisements used to recruit participants) and

any other necessary documents must be submitted, reviewed and approved by a properly constituted IRB governing each study location.

Any changes made to the protocol must be submitted as amendments and must be approved by the IRB prior to implementation. Any changes in study conduct must be reported to the IRB. The DF/HCC Overall Principal Investigator (or Protocol Chair) will disseminate protocol amendment information to all participating investigators.

All decisions of the IRB concerning the conduct of the study must be made in writing.

### **13.2 Informed Consent**

All participants must be provided a consent form describing this study and providing sufficient information for participants to make an informed decision about their participation in this study. The formal consent of a participant, using the IRB approved consent form, must be obtained before the participant is involved in any study-related procedure. The consent form must be signed and dated by the participant or the participant's legally authorized representative, and by the person obtaining the consent. The participant must be given a copy of the signed and dated consent document. The original signed copy of the consent document must be retained in the medical record or research file.

### **13.3 Ethics and Good Clinical Practice (GCP)**

This study is to be conducted according to the following considerations, which represent good and sound research practice:

- E6 Good Clinical Practice: Consolidated Guidance  
[www.fda.gov/downloads/RegulatoryInformation/Guidances/UCM129515.pdf](http://www.fda.gov/downloads/RegulatoryInformation/Guidances/UCM129515.pdf)
- US Code of Federal Regulations (CFR) governing clinical study conduct and ethical principles that have their origin in the Declaration of Helsinki

- Title 21 Part 11 – Electronic Records; Electronic Signatures  
[www.access.gpo.gov/nara/cfr/waisidx\\_02/21cfr11\\_02.html](http://www.access.gpo.gov/nara/cfr/waisidx_02/21cfr11_02.html)
- Title 21 Part 50 – Protection of Human Subjects  
[www.access.gpo.gov/nara/cfr/waisidx\\_02/21cfr50\\_02.html](http://www.access.gpo.gov/nara/cfr/waisidx_02/21cfr50_02.html)
- Title 21 Part 54 – Financial Disclosure by Clinical Investigators  
[www.access.gpo.gov/nara/cfr/waisidx\\_02/21cfr54\\_02.html](http://www.access.gpo.gov/nara/cfr/waisidx_02/21cfr54_02.html)
- Title 21 Part 56 – Institutional Review Boards  
[www.access.gpo.gov/nara/cfr/waisidx\\_02/21cfr56\\_02.html](http://www.access.gpo.gov/nara/cfr/waisidx_02/21cfr56_02.html)
- Title 21 Part 312 – Investigational New Drug Application  
[www.access.gpo.gov/nara/cfr/waisidx\\_02/21cfr312\\_02.html](http://www.access.gpo.gov/nara/cfr/waisidx_02/21cfr312_02.html)
- State laws
- DF/HCC research policies and procedures  
<http://www.dfhcc.harvard.edu/clinical-research-support/clinical-research-unit-cru/policies-and-procedures/>

It is understood that deviations from the protocol should be avoided, except when necessary to eliminate an immediate hazard to a research participant. In such case, the deviation must be reported to the IRB according to the local reporting policy.

#### **13.4 Study Documentation**

The investigator must prepare and maintain adequate and accurate case histories designed to record all observations and other data pertinent to the study for each research participant. This information enables the study to be fully documented and the study data to be subsequently verified.

Original source documents supporting entries in the case report forms include but are not limited to hospital records, clinical charts, laboratory and pharmacy records,

recorded data from automated instruments, microfiches, photographic negatives, microfilm or magnetic media, and/or x-rays.

### 13.5 Records Retention

All study-related documents must be retained for the maximum period required by applicable federal regulations and guidelines or institutional policies.

## 14 STATISTICAL CONSIDERATIONS

### 14.1 Study Design

14.2 **The single-arm protocol is a phase II study to investigate combining Losartan with FOLFIRINOX for induction chemotherapy followed by restaging and radiation therapy with capecitabine in the treatment of patients with locally advanced pancreatic cancer. The primary endpoint is the rate of R0 (negative margin) resection determined by final pathology of the surgical specimen. Our historical data show a <10% rate of R0 resection among unresectable patients treated with induction chemotherapy followed by chemoradiation. The protocol will have demonstrated an improvement in efficacy if R0 resection were achieved in at least 9 of 50 patients. The decision rule is associated with 91% power if FOLFIRINOX-Losartan with short-course radiation and capecitabine were to improve the R0 resection rate to 25%. In contrast, the probability of a type 1 error is only 6% if the underlying rate of R0 resection were truly the same as the historical level of 10%. All protocol patients who start induction chemotherapy will be included in the denominator for R0 resection analysis, including those who do not undergo surgery due to early progression or other reasons. Sample Size/Accrual Rate** The accrual goal of 50 patients is projected to be enrolled over a total period of 4.5 years. The estimate is based on the overall rate of accrual based on the first 32 patients since the protocol was first open to patient entry. Therefore, we project the enrollment of the remaining 18 patients will require no more than 1.5 years.

### 14.3 Analysis of Secondary Endpoints

- 14.3.1 **Progression-free survival:** All patients who start induction chemotherapy will be analyzed based on the definition in Section 10.1.2. The progression-free survival duration of patients who are alive and progression will be censored at their date of last follow-up. The Kaplan-Meier method will be used to estimate progression-free survival with 90% confidence intervals constructed by Greenwood's formula.
- 14.3.2 **Overall survival:** Overall survival will be defined as the duration between the start date of protocol therapy and death. The survival time of patients who are not known to have died will be censored at the date they are last known to be alive. The Kaplan-Meier method will be used to estimate overall survival estimation with 90% confidence intervals constructed by Greenwood's formula.
- 14.3.3 **Toxicities:** All patients who begin induction chemotherapy will be included in the toxicity profile of Losartan combined with induction FOLFIRINOX. Summaries of toxicities will include the frequency and proportion of patients experiencing each toxicity, as well as summaries by toxicity category and toxicity grade. We shall report separately the additional treatment-related toxicity following radiation in patients who do not have progressive disease at the restaging interval after induction chemotherapy.
- 14.3.4 **Downstaging:** A fraction of patients may proceed to surgical resection following the conclusion of protocol therapy if the tumor shrinkage were sufficient to be considered resectable. The rate of downstaging to surgical resection will be determined as the proportion of initially unresectable patients who eventually undergo pancreaticoduodenectomy or distal pancreatectomy. The pathologic downstaging rate will be calculated as the proportion of resected patients with the primary tumor and nodes downstaged based on final pathology of the surgical specimen.
- 14.3.5 **Correlation of biomarkers with outcome:** Correlative studies will be conducted to characterize circulating collagen and angiogenesis biomarkers (8.1.1), as well as somatic genetic mutations characterized by the SNaPshot platform (8.1.2). Due to the modest patient numbers, analysis will be limited generally to two-group comparisons of each

biomarker. Continuous values will be dichotomized at the median or a biologically meaningful threshold. The logrank test will be used to assess differences in progression-free survival and overall survival by biomarker status if at least 5 failure events have been observed within each subgroup. The correlative analysis will be purely exploratory due to the limited numbers expected per biomarker subgroup. In particular, analysis will be descriptive when the frequency of a genetic mutation is low.

14.3.6 ***Patient-reported outcomes***: We will use descriptive statistics to describe QOL (EORTC QLQ-C30), symptom burden (ESAS-r) and mood (HADS) for the entire study cohort. Mean values and standard deviations will be used to describe QOL and symptom burden (T-test or Wilcoxon as appropriate). We will score the HADS subscales for depressive and anxiety symptoms categorically, using a cut-off of >7 to describe the proportion of patients with these symptoms. We will use Chi-square or Fisher's Exact Test, as appropriate, to analyze the categorical variables.

14.3.7 ***Health care utilization***: We will use descriptive statistics to describe hospitalizations, ICU stays, ED visits and palliative care use for the entire study cohort. Mean values and standard deviations will be used to describe continuous variables (T-test and Wilcoxon rank sum, as appropriate). We will use Chi-square or Fisher's Exact Test, as appropriate, to analyze the categorical variables.

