### **5.6 Duration of Follow Up**

Patients will be followed until documented progression, at which time they will be followed for survival only. Participants removed from study for unacceptable adverse events will be followed until resolution or stabilization of the adverse event.

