**Required Data Table**

Tests and Observation	Prior to treatment	Cycles 1-8 of FOLFIRINOX/Losartan	After cycles 4 and 8 of FOLFIRINOX/Losartan (re-staging) (5)	Radiation	Follow Up Post-Proton RT (2)
Signed informed consent	X				
History	X				
Physical Examination	X	X once per cycle	X	X weekly	X
Vital Signs and performance status	X	X once per cycle	X	X weekly	X
Height/Weight/Surface Area	X	X once per cycle			
Blood Pressure Assessments and Monitoring	X	X once per cycle			
Toxicity Assessment	X	X weekly during cycle 1; every other week during subsequent cycles unless clinically indicated	X	X weekly	X
Laboratory :					
CBC/plts/diff	X (1)	X weekly during cycle 1; every other week during subsequent cycles unless clinically indicated	X	X weekly	X
Serum chemistries (Na, K, BUN, Cr, Glucose, , Calcium, Albumin, AST, ALT, Total bilirubin, Alkaline phosphatase)	X (1)	X weekly during cycle 1; every other week during subsequent cycles unless clinically indicated	X	X weekly	X

Phase II Study of FOLFIRINOX-Losartan with Short Course Radiation and Capecitabine in Locally Advanced Pancreatic Cancer August 7, 2018

Tests and Observation	Prior to treatment	Cycles 1-8 of FOLFIRINOX/Losartan	After cycles 4 and 8 of FOLFIRINOX/Losartan (re-staging) (5)	Radiation	Follow Up Post-Proton RT (2)
Creatinine clearance calculation (Cockcroft Gault)	X (1)	X weekly during cycle 1; every other week during subsequent cycles unless clinically indicated	X	X D1 and D8 of capecitabine	
CA19-9	X (1)	X Monthly	X		X
CEA	X (1)	X Monthly	X		X
Pregnancy test*	X (1)				
Research Blood for Correlative Analysis: Antifibrotic Effect (6)		X D1 (pre-treatment), D8, D29, and D92			
Tumor submitted for SNaPSHOT mutational analysis	X				
Staging:					
Chest CT Abd-pelvic CT (or MRI)	X (3)	X Mid-treatment and post-treatment	X		X (4)
Radiation Planning				X prior to RT start	
Tumor measurements (8)	X		X		X
PRO (EORTC QLQ-C30, ESAS-r, HADS) (7)	X	X	X	X	X

Notes

- (1) Pre-study Laboratory values need to be obtained within 7 days of study entry.
- (2) Post-study follow up schedule is clinic visit and labs every three months until disease progression. The first visit will be 1 month after surgery. Then follow up visits will be every 3 months. CT scans will be at least every six months for the first two years and yearly for years 3-5. All follow up assessments will be performed +/- 21 days of protocol-specified date.
- (3) Staging CT or MRIs need to be obtained within 42 days of study entry

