- (4) CT scans will be performed at least every 6 mo for the first 2 years and yearly for years 3-5. All follow up CT scans will be performed +/- 21 days of protocol-specified date
- (5) Restaging scans can be performed after pump disconnect during FOLFIRINOX cycles 4 and 8.

- (6) Blood for correlative studies will be obtained with clinical labs at pretreatment, day 8 of Cycle 1 FOLFIRINOX, at mid-FOLFIRINOX restaging, at post-FOLFIRINOX restaging, after chemo radiation therapy, 1 month after completion of capecitabine therapy, 1 month post-operatively (if surgery is performed), and within two weeks of radiographic progression (these blood draws are optional).
- (7) See section 8.2 for patient reported outcomes assessment timing.
- (8) Tumor measurements will be completed within +/-6 months of the scans. These measurements will be completed by the overall PI of the study.

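### Section 14.3.1 censors PFS at last follow-up rather than at the last tumour assessment, so unscanned time counts as progression-free; the effect is small and cheap to remove

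*Combined protocol and SAP*

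**What the plan says.** - **Censoring.** Section 14.3.1 states that "patients who are alive and progression will be censored at their date of last follow-up". The sense must be alive without progression. For overall survival, 14.3.2 uses different words: patients "will be censored at the date they are last known to be alive". Last follow-up is not defined.
- **Event.** Section 10.1.2 runs PFS from the start of protocol therapy to objectively documented progression or to death. It does not say whether the scan date or the date the scan was measured counts.
- **Scans and visits.** Section 5.1 restages after cycles 4 and 8. After that, note (2) to the Study Calendar asks for "clinic visit and labs every three months until disease progression", and note (4) says that "CT scans will be performed at least every 6 mo for the first 2 years and yearly for years 3-5". Follow-up assessments have a window of +/-21 days.
- **Follow-up.** Section 5.6: "Patients will be followed until documented progression, at which time they will be followed for survival only".
- **Measurement timing.** Calendar note (8): "Tumor measurements will be completed within +/-6 months of the scans". Section 12.1.2 wants the tumour measurement form "within 14 days of protocol defined restaging assessment" and the follow-up form "Within 14 days of the protocol defined follow up visit date".
- **Analysis.** Kaplan-Meier with 90% Greenwood intervals. Section 14 has no rule for missed scans and no PFS sensitivity analysis.

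**The concern.** A patient can be known to be free of documented progression only up to the last assessment able to show it. If the censoring date is a later clinic visit, the patient stays in the risk set for months in which progression was not looked for by imaging. That raises the Kaplan-Meier curve. The same can happen when a patient comes off treatment for toxicity: section 5.6 follows such patients until the adverse event resolves or stabilises, so their last follow-up could be a safety contact without a scan.

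PFS is the first secondary objective (1.3.1) and one of the two endpoints for the biomarker logrank comparisons in 14.3.5. Because the term is undefined, two analysts could choose different censoring dates from the same data.

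**Working it through.** **Figures in the plan.** The plan gives no expected PFS, PFS target or PFS test, so there is no PFS figure to reproduce. Its R0 figures do reproduce: the rule of at least 9 of 50 has exact binomial type I error 0.0579 (stated 6%) and power 0.9084 at 25% (stated 91%). PFS does not enter either.

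**How far the last visit can lie beyond the last scan.** On nominal dates, with 3-monthly visits:

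- years 1-2: 6 - 3 = 3 months
- years 3-5: 12 - 3 = 9 months
- with an early scan and a late visit, the windows add 2 x 21 = 42 days, about 1.4 months, so 3 becomes about 4.4

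Missed scans can lengthen these gaps. Extra scans, which the words at least allow, shorten them.

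**What the rule does to the estimate.** This was simulated with 200,000 patients per scenario. From the documents: restaging at about months 1.84 and 3.7, then the minimum CT schedule with +/-21 days, 3-monthly visits and 54 months of accrual. Assumed, not in the documents: exponential progression; median 8 months from progression to death; 3% per year death without progression; 6-monthly CT counted from the post-cycle-8 scan; loss to follow-up of 5% per year with 12 months of extra follow-up, or 20% per year with none. The rows below also assume that half of progressions are found at the next 3-monthly visit.

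| Progression median (months) | Loss per year | 12-month PFS: last follow-up | 12-month PFS: last scan | Difference (points) | Median: last follow-up / last scan |
|---|---|---|---|---|---|
| 10.8 | 5% | 51.0% | 50.4% | 0.6 | 12.7 / 12.6 |
| 10.8 | 20% | 50.4% | 48.6% | 1.8 | 12.6 / 10.3 |
| 15 | 5% | 61.1% | 60.6% | 0.5 | 15.7 / 15.7 |
| 15 | 20% | 60.6% | 59.0% | 1.6 | 15.7 / 15.5 |

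Across the scenarios (medians 6.4 to 15) the 12-month difference was 0.5 to 0.7 points with 5% loss and 1.4 to 1.8 with 20%. The median usually moved by 0 to 0.2 months. It moved by 0.8 to 2.3 months only in some 10.8-month scenarios. The second row shows why: events cluster around the CT near month 9.7, the curve is then nearly flat close to 50%, and 1.8 points decide on which side of the flat stretch it crosses.

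**Dependence on the data cut.** With n = 50, 400 trials per scenario, no loss to follow-up, and 0, 50 or 100% of progressions found at visits, the rule alone added to the median:

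- 24 months' minimum follow-up: 0
- 12 months: 0 to 0.28
- 6 months: 0.03 to 0.54
- cut on the day of last entry: 0.04 to 0.70 (middle scenario 0.19)

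**The part due to scan spacing.** In the first row, Kaplan-Meier on true progression times gives 44.9% at 12 months. Last-scan censoring gives 50.4%, so spacing accounts for 50.4 - 44.9 = 5.5 points and the censoring rule for 0.6. Across scenarios spacing accounts for about 3 to 6 points at 12 months. The balance changes later: at 24 months the two parts are of similar size, and with 20% loss the rule is the larger.

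**Side effect of the replacement.** At 24 months with 20% loss, true PFS is 20.2% (10.8-month rows) and 31.2% (15-month rows). Last-follow-up censoring gives 22.0% and 33.0%, which is 1.8 points high in both. Last-scan censoring gives 19.7% and 30.3%, which is 0.5 and 0.9 points low.

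**The case against.** The strongest reply is that the endpoint in 10.1.2 is time to documented progression, and Kaplan-Meier estimates that quantity properly under the planned CT schedule. This stands, and it removes the more alarming reading. A reader might infer that 14.3.1 inflates median PFS by months: with n = 50 the planned median exceeds the true-progression median by 0.9 to 4.3 months across the assumed scenarios. That is of the same order as its 90% half-width, 1.645 x median / (ln 2 x sqrt 50): 2.1 months at a median of 6.4 and 3.6 at 10.8 (exponential, no censoring). But nearly all of the excess is scan spacing, measured against an event date that the plan does not claim to observe, and no wording in 14.3.1 would remove it. The upper end also assumes no imaging beyond the minimum.

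It is also fair that the part due to the rule is small and that a cut on the day of last entry is unrealistic, because R0 status needs eight cycles, radiation, surgery and pathology. Against that, the zero at 24 months' minimum follow-up assumes no patient is lost. With loss the rule has an effect at any cut.

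Two further inferences go too far. Note (8) is a window for completing measurements; the plan does not adopt the measurement date as the progression date. And last follow-up need not mean any contact: 5.6 separates disease follow-up from survival-only follow-up, and 14.3.2 words its own rule differently. Both are ambiguities to close, not rules to criticise.

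**Conclusion.** The point holds as a cheap improvement. As written, 14.3.1 counts time after the last scan as progression-free. Under the assumptions above this is worth about 0 to 2 points of 12-month PFS and usually 0 to 0.3 months of the median, more only where the curve is flat near 50%, and essentially nothing with long, complete follow-up. The documents give no expected PFS, loss rate or detection pattern, so these are ranges and not predictions.

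That documented progression comes later than true progression is a property of the CT schedule, driven mainly by the first 6-month gap after induction. It belongs in the reporting of PFS. No direction is claimed relative to trials with other scan intervals. The primary R0 conclusion is unaffected.

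**What to change.** In 14.3.1:

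1. Correct the sentence to *alive and progression-free*, and censor at the date of the last evaluable tumour assessment, or at the start of therapy if there is none.
2. Date progression at the scan or other objective evidence that first shows it, not at the date of measurement, and reconcile calendar note (8) with 12.1.2.
3. Record the date of each follow-up CT on the follow-up form. Section 12.1.2 ties the tumour measurement form to registration and restaging, and the follow-up form to the visit date.

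When PFS is reported, state the CT schedule and that the estimate is time to documented progression.

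An interval-censored sensitivity analysis is optional and should carry no claim to reduce bias. In a check with n = 50 and 24 months' minimum follow-up, a Turnbull median erred by -1.2 to +1.8 months, against +0.9 to +3.7 for Kaplan-Meier, and by -1.2 to 0.0 when visits found every progression.

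The cost is a few lines of text, one form field if it is not already there, and a little programming, with no extra scans. Reported PFS may be slightly lower, and with heavy early loss last-scan censoring may read slightly low at late time points.
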